While there is compelling evidence demonstrating the benefits of weight-loss interventions for both diabetic and pre-diabetic individuals, Hispanic participants typically lose less weight than non-Hispanic white participants, even in successful trials. Furthermore, most large randomized trials have selected only adherent individuals, using strict filtering criteria that screen out individuals generally considered poor candidates for retention.⁴⁶⁻⁴⁹ Many of the successful interventions tested in clinical trials may be too resource-intensive for implementation in community settings⁴⁰ and often include costly incentives, meal replacement products⁴⁰ or home visits.⁵⁰

The current study will be implemented in a federally qualified health center (the Virginia Garcia Memorial Health Center, VGMHC) primarily serving low-income Hispanic patients. We will compare the efficacy of a culturally competent group intervention targeting Hispanic women with impaired glucose regulation (diabetic and prediabetic patients), contrasting it with a usual care control condition. The intervention we will be testing is modeled on an intervention program for obese Mexican-American women we previously conducted at KPNW CHR.¹⁴ Our study will assess the cost of the intervention within the context of the clinical trial, and will assess the feasibility and cost of implementation in the absence of research support.

To ensure that this intervention is viable, sustainable, and able to be disseminated, and not merely a one-time research project, the program will be conducted by Virginia Garcia clinic staff, with training, supervision and support, and a minimum of “scaffolding” provided by the research team. Following the clinical trial, and at the request of VGMHC we will assess the sustainability and cost of the intervention as delivered by the interventionists without support from research staff.

Aims

1. Assess short (6-month) and long-term (12- and 18-month) changes in body weight and waist circumference in women in the intervention group compared to an enhanced usual-care control group

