2. Compare the effects of the intervention vs. enhanced usual-care control on secondary outcomes, including short- and long-term changes in diabetes and prediabetes-related outcomes of metabolic markers of glycemic control (a) hemoglobin A1c, and (b) fasting glucose; cardiovascular disease risk factors: (c) fasting lipid profile; and lifestyle outcomes: (d) dietary intake (total energy, simple carbohydrates, saturated fat, number of servings of fruits and vegetables, dietary fibers, and whole grains), and physical activity.
3. Determine the implementation cost of delivering this weight-loss intervention at a Federally Qualified Health Center in the context of a pragmatic clinical trial.

Research Design

This will be a randomized clinical trial testing a weight-loss lifestyle intervention for obese Hispanic women with prediabetes or T2D. The primary aims of the intervention will be to reduce body weight and waist circumference at 6, 12, and 18 months. Secondary aims will be to improve levels of HbA1c, markers of glycemic control (fasting glucose in addition to HbA1c) and cardiovascular disease risk (serum lipid profile), diet, and physical activity. We will also determine the implementation cost for delivering the trial intervention in a federally qualified health center. Following the clinical trial, through a 2-cohort phase, we will assess the sustainability and cost of delivering the intervention as part of regular patient care at the clinic in the absence of research support.

Trial participants will be randomly assigned to one of two conditions: 1) Enhanced usual care control, or 2) a culturally tailored behavioral intervention. Outcome assessments will be conducted at 6, 12, and 18 months. Recruitment will be conducted in seven cohorts of approximately 30 randomized participants each.

Each participant will receive a \$25 gift card at the completion of the 6-month visit, \$30 at 12-month and \$35 at 18-month data collection points.

Eligibility

We will enroll 200 obese Hispanic women in this weight-loss intervention trial.

Inclusion criteria.

- All participants will be patients who receive their primary medical care at the Virginia Garcia Memorial Health Center (VGMHC)
- Self-identified as Spanish-speaking Latina or Hispanic
- Female
- Age 18 and older
- BMI greater than or equal to 27kg/m²
- Classified as diabetic or prediabetic in the electronic medical record by *at least one* of the following:
 - o Fasting plasma glucose ≥ 100

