 - o 2-h post glucose level on the 75-g oral glucose tolerance test $\geq 140-199$ mg/dL (7.8-11.0 mmol/L)
 - o Hemoglobin HbA1c ≥ 5.7
 - o Diagnosis of diabetes in patient's medical chart

- Diagnosis of prediabetes in patient's medical chart
- Residing in the Portland metropolitan area, and having no plans to leave the area in the next 18 months.
- Willing and able to attend the 26-weekly group meetings and 6 monthly group meetings.
- Willing to accept random assignment to the active intervention or enhanced usual care control.
- Clearance by the patient's VGMHC primary care physician to participate in the intervention.

Exclusion criteria

- Treatment for cancer in the past two years (excluding non-melanoma skin cancers).
- Having conditions that require limitation of physical activity or that would be contraindicated for the DASH diet patterns.
- Taking weight-loss medication currently or within the past 6 months.
- Current or recent (\leq 12 months) pregnancy, breastfeeding, or planning pregnancy in the next 18 months.

Recruitment

After attending an explanatory session as part of the informed consent process, each participant will sign the IRB-approved, written, bilingual, study consent prior to being enrolled in the study. The consent form will describe the purpose of the study, the requirements for participation, and the potential benefits and risks. It will also document that participation is voluntary, that it may be terminated by the participant at any time, and that decision to participate will not affect the clinical care received at VGMHC.

Potentially eligible patients from VGMHC will be identified through a review of the electronic medical record and through direct physician referral. Potentially eligible patients will be mailed a written description of the study and a consent form to review. Recruitment materials will be provided in both Spanish and English. Interested women will be invited to call the research center for more information, and those who are not interested in participating will be able to decline by telephone or by mail. Those who do not respond to the mailing may be called by a bilingual project staff member and asked about their interest in the study.

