The change in consent will affect about 90 participants. Participants in the intervention groups will receive their new consent at one of the sessions. Usual care participants will receive a phone call from [name] alerting them to watch for the form in the and if desired discuss the change in the consent.

Prior to randomization, participants will be required to obtain medical clearance for participation from their VGMHC health care provider.

Baseline Data Collection and Randomization

After completing the baseline telephone assessments, participants will be scheduled for a randomization visit at VGMHC. During this visit we will collect baseline measurement of fasting lipids, glucose, and HbA1c as they are done in the course of clinic operations at VGMHC, by

finger-stick using point-of-care devices. Participants will then receive their treatment assignments using a computerized block randomization scheme provided by the study statistician. Randomization will be stratified by baseline BMI (27-34, 35-39, 40 or more) and age (18-45, 46 and above). To ensure equal balance in the two arms, randomization will occur in block sizes of 4. Participants will be informed of their randomization assignments by intervention staff members. Data collection staff will be masked to treatment assignments.

Enhanced Usual Care Control

We considered using a no-treatment control condition, but our community clinic partners requested that we provide the same information to participants in both conditions. This strategy insures that all participants get something they value as part of their involvement in the study, and also provides a comparison of the lifestyle intervention program to a very low-cost and easy to deliver information-only program.

Weight Management Tools for All Trial Participants

So that all randomized participants receive the same basic information, those assigned to the enhanced usual care control condition will receive bilingual printed materials on how to improve weight-related behaviors: copies of the NHLBI “Steps to Lose Weight,” “ChooseMyPlate,” and “Nutrition and Finding Your Way to a Healthier You.” We recognize that literacy limitations may be an issue for some participants, but providing this type of printed material is our approximation of the best current “usual care” practice. In addition to this written material, all participants in both arms of the trial will receive:

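### A single block size of 4, printed in the protocol, would let someone who tracks assignments by stratum know up to about a third of allocations in advance

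*Combined protocol and SAP*

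**What the plan says.** *Baseline Data Collection and Randomization* sets out the method: "Participants will then receive their treatment assignments using a computerized block randomization scheme provided by the study statistician". Three BMI bands are crossed with two age bands, and "To ensure equal balance in the two arms, randomization will occur in block sizes of 4". *Research Design* names two arms; 1:1 allocation is inferred from the stated aim of equal balance.

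On who knows the arm, the same section says: "Participants will be informed of their randomization assignments by intervention staff members". *Recruitment* says the same of the randomization visit. Masking is stated for data collection staff only.

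The setting is one health center. The background says that "the program will be conducted by Virginia Garcia clinic staff". Under *Recruitment*, candidates are found "through a review of the electronic medical record and through direct physician referral". Each woman also needs clearance from her own provider at that health center before randomization. Height and weight are measured at the consent visit, ahead of the telephone interview and the individual randomization visit.

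The documents do not say who holds the list, how the next assignment is concealed, whether the block size is withheld from staff, or who schedules randomization visits. They also do not say whether staff who know assignments are kept apart from enrolment.

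**The concern.** In a fixed block of four with two places per arm, the rest of the block is determined once either arm has its two. Anyone who knows the block size and the earlier assignments in a stratum can then name the next arm. Age, and normally the BMI band, are known from the consent visit, so the stratum of a woman waiting for her randomization visit can usually be worked out beforehand. Masking the data collectors protects outcome measurement; it does nothing to conceal the sequence from those who deliver it.

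What is at stake is selection before assignment. Someone who foresees the next arm could bring forward, delay or discourage a woman's visit according to how likely she seems to attend the groups. If likely attendance is related to weight loss (an assumption; the documents give no figure), the arms would differ in a prognostic factor that the analysis does not hold. The 6-month model in *Statistical Analysis* contains only the baseline value of the outcome and study arm. The long-term model contains time, arm and their interaction.

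**Working it through.** The plan gives no predictability figure, so there is none to reproduce.

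**Inputs.** Block size 4 and 3 × 2 = 6 strata (*Baseline Data Collection and Randomization*); two arms, and seven cohorts of about 30, so about 210 (*Research Design*); 200 women (*Eligibility*); 1:1 allocation (inferred).

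**Step 1: complete blocks.** There are C(4,2) = 6 equally likely orderings. An allocation is certain when one arm has already filled its two places.

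| Position | Probability certain | Probability best guess is right |
|---|---|---|
| 1 | 0 | 1/2 |
| 2 | 0 | 2/3 |
| 3 | 1/3 | 2/3 |
| 4 | 1 | 1 |
| Sum | 4/3 | 17/6 |

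Certain: (4/3)/4 = 33.3%. Best guess right: (17/6)/4 = 2.83/4 = 70.8%, against 50% with no information.

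**Step 2: unfinished final blocks.** Compared with n/3, a stratum whose last block holds 0, 1, 2 or 3 women falls short by 0, 1/3, 2/3 or 2/3 certain allocations. If the four cases are equally likely, the mean shortfall is (0 + 1/3 + 2/3 + 2/3)/4 = 5/12. Over six strata this is 6 × 5/12 = 2.5. So 200/3 − 2.5 = 64.2 allocations are certain, and 64.2/200 = 32.1%. Simulation gave 32.1% with equal stratum shares and with uneven ones (35, 20, 10, 20, 10 and 5%; assumed).

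**Step 3: lists restarted in each cohort (not stated; an assumption).** There would be 6 × 7 = 42 lists. Then 210/3 − 42 × 5/12 = 70 − 17.5 = 52.5, and 52.5/210 = 25.0%.

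**Step 4: an observer who ignores strata.** Counting in fours over the whole trial, such an observer would be right only about 54% of the time when an allocation looked certain (simulation, six equal strata). The one-third figure therefore requires tracking within each stratum.

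**Step 5: randomly varying block sizes.** Take 34 women per stratum (200/6 = 33.3, rounded up). Fixed blocks of 4 give 8 full blocks plus 2 women:

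- certain: 8 × 4/3 = 10.67, and 10.67/34 = 31.4%;
- best guess right: 8 × 17/6 + 1/2 + 2/3 = 23.83, and 23.83/34 = 70.1%.

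The mixes were simulated (2,000 lists each) against an observer who knows the set of sizes and every earlier assignment in the stratum, but not where blocks begin.

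| Scheme | Certain | Best guess right |
|---|---|---|
| Fixed 4 | 31.4% | 70.1% |
| Random 4 and 6 | 5.7% | 68.8% |
| Random 4, 6 and 8 | 2.3% | 67.5% |

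**Step 6: cost in balance.** The largest possible within-stratum difference is half the largest block: 4/2 = 2 now, 6/2 = 3 with a 4/6 mix, 8/2 = 4 if blocks of 8 are included.

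**The case against.** A reader might infer that intervention staff hold a running list by stratum, will therefore know a third of allocations, and can act on this because the same clinic refers, clears and schedules the women. The documents do not support that. They say only that intervention staff deliver assignments; no section gives those staff a list, shows them the strata, or has one person deliver every assignment. The scheme is computerized and comes from the statistician. Recruitment calls are made by project staff, consent is taken by study staff, telephone interviews are done by research-center staff, and clearance comes from the woman's own provider. Nothing says that referring or clearing providers see assignments.

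The practical room is also limited. Six strata must be followed in parallel. A cohort of about 30 averages 30/6 = 5 women per stratum, so there are few visits to reorder. Weight is measured again at the randomization visit, and the documents do not say which weight sets the BMI band, so a woman near a boundary may change stratum. Consent, clearance and baseline measurement already precede assignment.

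These points make one third a ceiling and leave the route to bias unproven. They do not remove the gap: the block size is fixed and printed, staff who know both arms' assignments work at the same health center, and no separation of roles or concealment procedure is stated.

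It can also be objected that varying the block size barely changes the best-guess rate. That is correct, and it is why the change of block size should not stand alone.

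**Conclusion.** The concern holds as a risk of selection bias that is cheap to reduce. For an observer tracking all six strata, up to about a third of allocations are certain: 33.3% for complete blocks, about 32% over 200 women, and about 25% if the lists restart in each cohort. The figures assume 1:1 allocation, knowledge of the block size, and complete knowledge of earlier assignments by stratum.

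It would be wrong to conclude that selection has occurred or that the arm comparison is biased. The documents give no sign of either, and no bias in kilograms can be derived from them. Fixed blocks of 4 are a design choice, neither an internal contradiction nor an analysis error, so this is a low-cost improvement rather than a threat to the trial's conclusions.

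The part still open to change may be smaller than the whole trial. *Explanatory Session and Consent Visit* says that a consent revision affects about 90 participants and describes them by arm. If they are already randomized (an inference), about 200 − 90 = 110 women remain, of whom at most about 110/3 = 37 would have a certain allocation under the present scheme.

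**What to change.** For women not yet randomized, replace the block-size sentence with wording such as:

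> *Allocation will use stratified permuted blocks of randomly varying size, generated by the study statistician. Block sizes will not be disclosed to clinic, recruitment or intervention staff. Staff who know treatment assignments will take no part in enrolment or in scheduling randomization visits.*

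A mix such as 4 and 6 would serve. The sizes actually used should be recorded only in a restricted document held by the statistician, and the figure of 4 should come out of any copy that staff can see. One more sentence should say who holds the list and how the next assignment is released. The present order, with baseline measurement before assignment, needs no change.

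The cost is regenerating the remaining list, a few sentences of protocol text, and a maximum within-stratum imbalance of 3 instead of 2 with a 4/6 mix. If recruitment is already complete, the sponsor should instead document how concealment was achieved and which staff could see assignments.

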Participants assigned to the usual care control condition will receive printed materials (in English and/or Spanish) developed by the NHLBI on how to improve weight-related behaviors ("Steps to Lose Weight," "ChooseMyPlate," "Nutrition and Finding Your Way to a Healthier You"). We recognize that literacy limitations will reduce the usefulness of these materials for some of our participants, but providing this type of printed materials is our approximation of the best "usual care" practices currently available at VGMHC. Participants in both the intervention and the enhanced usual care control arms will receive a bathroom scale, a set of measuring cups and spoons, and a pedometer (with printed instructions and tips for increasing physical activity).

Follow-up data for all randomized participants will be collected at 6, 12 and 18 months following randomization. Physical data collection (height, weight, waist circumference, blood draws) will be completed at the VGMHC clinic; all other data collection will be done by telephone interview. All data-collection staff will be female and bilingual, and masked to participant treatment assignment.

Explanatory Session and Consent Visit

Explanatory sessions will be conducted by a bilingual study staff member who will provide a thorough overview of the study, including the intervention, design, and requirements for weekly group meetings, planned data collection, and duration of follow up. Attendees will be encouraged to ask questions. Then, the study consent will be discussed, and women interested in enrolling in the study will meet individually with study staff to address additional questions, confirm eligibility, and sign the consent form. Those who consent will be measured for height and weight, and will be scheduled for baseline bilingual assessment interviews conducted by telephone in the next 2 weeks. The telephone baseline assessment will include a food frequency questionnaire and physical activity questionnaire.

Participants may take their consent home to return at a later time but must return to the VGMHC with their consent form, to be witnessed and signed, and have their baseline measurements taken.

We have revised the consent to include sharing of participants PHI with Arizona State University. PhD candidate students in the Department of Nutrition will conduct the follow up SW FFQ interviews and, if needed due to literacy issues, conduct the Follow Up visit questionnaire by phone.

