Bathroom Scale: As found in other studies,³⁸ our research experience has been that few Hispanic women self-weigh regularly, and most do not own a scale. To aid in self-monitoring, all participants will be provided with a digital bathroom scale.

Pedometer: A pedometer and printed bilingual instructions for its use and tips for increasing PA will be provided to help participants monitor daily steps. We will not use pedometers for outcome data collection.

Measuring cups and spoons: Our pilot work has shown that many Hispanic women are unfamiliar with Anglo-American food measurements.¹⁴ Traditional Latin American cooking practices rarely use measuring cups and spoons. To help participants measure their food, all participants will be provided with a set of measuring cups and spoons, along with a printed equivalence table (Anglo-American measuring units and metric units).

Retention

To maximize participant retention, during the screening process will we provide oral and written information about study expectations, time commitment, schedule and length of intervention group sessions, and potential benefits and risks. To enhance completion of the assessment visits, we will use appointment reminders (letters and phone), and schedule visits at times as convenient as possible to the participant.

Weight Loss Intervention

The initial intervention will consist of weekly meetings for 6 months, as recommended by Wadden.⁹³ The meetings will be structured to be very interactive, involve participant input and group activities, foster problem solving, support, and program ownership. We are planning for approximately 15 participants per group; groups of similar size have been shown to be quite effective in previous weight-loss studies.^{3,25}

Each session will have a similar structure with 6 main components:

1. Social support/group sharing
2. Review of each individual's progress since the last session
3. Main content area (e.g., meal patterns, calories)
4. Behavioral skills training
5. Goal setting and action plans (in small groups)
6. Plans of self-monitoring activity

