The weight loss program is designed to achieve weight loss through dietary calorie reduction, increased energy expenditure through physical activity, and improved self-efficacy through behavioral self-management.

Dietary recommendations:

1. Consume ~500 fewer calories per day to achieve ½-2 lb weight loss per week.
2. Eat a healthy dietary pattern (i.e., the DASH eating style and WLM program, a diet rich in fruits, vegetables, and low-fat dairy foods, and low in fat).
3. Limit alcohol consumption to no more than one drink per day.

Physical activity recommendations:

4. In addition to normal daily activities, exercise at moderate intensity most days per week.
5. Progress gradually to 30-60 minutes/day to a weekly target of at least 180 minutes.

Behavioral recommendations:

6. Record daily food intake and physical activity.
7. Set short-term goals and create action plans.
8. Be an active study participant by attending intervention group sessions.

Measures

Weight will be measured with participants in light indoor clothes without shoes, and determined to the nearest 0.1 kg by a calibrated digital scale.

Height will be measured at enrollment to the nearest 0.1 cm using a calibrated, wall-mounted stadiometer.

Waist circumference will be measured at the midpoint between the lower rib and the iliac crest. We will record this to the nearest 0.5 cm. Measurement will be done with a Linen non-stretch tape measure with a tension device to provide a constant tension during measurement.

HbA1c and fasting lipids, and glucose will be collected in the course of patient care, using point-of-care devices to facilitate data collection by VGMHC staff members. Data will be collected for all trial participants at baseline, 6-, 12-, and 18-months post randomization. For participants that are unable to come to the clinic for the blood draw, we will do a home outreach and collect the sample at their homes.

Fasting lipids (total cholesterol, HDL-cholesterol, and triglycerides) will be measured enzymatically (Lipid Panel Plus Reagent Disc; Henry Schein, Inc, Melville, NY) in whole blood using a Piccolo Blood Chemistry Analyzer (Abaxis Inc., Union City, CA). LDL-cholesterol will be calculated using the Friedewald equation.⁹⁶ Fasting

glucose will be measured using a OneTouch Ultra blood glucose monitoring system (LifeScan, Inc. Milpitas, CA). HbA1c will be measured from capillary blood using an A1cNow+ device (Bayer HealthCare LLC,

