department maintains CHR's data management hardware, software, security, storage, and networking resources. Standard data management procedures include Manuals of Operations, logging of forms, and work performance and quality control functions. Data management protocols include creation of a detailed plan for each instrument covering design, coding, pre-testing, preparation, administration, entry, verification, data set cleaning, and basic descriptive statistics. Procedures for data editing, entry, verification, and summarization are well-established at CHR. [name], the study statistician, and the project manager will work closely to establish and monitor the data management procedures for this study. The study statistician will perform or directly oversee all data analyses.

Statistical Analysis

Before any analyses are carried out, the data will be audited for quality, completeness, and evaluation of distributions with reference to planned analysis models. The evaluation of distributions will include the detection of outliers in quantitative data and checking distributions of variables to ensure that they meet the assumptions of planned analyses. Whenever possible we will use analytical techniques that allow us to keep the natural distribution of the variables, but will consider transformation if necessary.

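### The 6-month test has no missing-data rule and cannot use a woman measured only at 12 or 18 months; secondarily, home outreach is written for blood but not for weight or waist

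*Combined protocol and SAP*

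**What the plan says.** **Analysis (Statistical Analysis).** The main analysis is described as intention to treat. For 6 months, the dependent variable is change from baseline to that visit, and the predictors are the baseline value and an arm indicator. For the long term, a multilevel model with quadratic time uses baseline, 6, 12 and 18 months. Both approaches extend to waist. The nearest text to a missing-data rule is that "the data will be audited for quality, completeness, and evaluation of distributions with reference to planned analysis models". That is a data check, and it does not say how a missing weight is analysed.

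**Collection (Recruitment, follow-up paragraph).** "Follow-up data for all randomized participants will be collected at 6, 12 and 18 months following randomization". The default place is the clinic: "Physical data collection (height, weight, waist circumference, blood draws) will be completed at the VGMHC clinic". Also, "All data-collection staff will be female and bilingual, and masked to participant treatment assignment".

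**Home outreach (Measures, paragraph on blood tests).** For participants "unable to come to the clinic for the blood draw, we will do a home outreach and collect the sample at their homes". The weight and waist paragraphs of the same section describe a calibrated scale and a tape with a tension device, and do not mention home use.

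**Contact and retention.** In the active arm, "The initial intervention will consist of weekly meetings for 6 months" (Weight Loss Intervention). "Participants assigned to the usual care control condition will receive printed materials" (Recruitment), and both arms receive a scale, pedometer and measuring tools. For assessment visits in both arms, "we will use appointment reminders (letters and phone), and schedule visits at times as convenient as possible to the participant" (Retention), and each follow-up visit carries a gift card (Research Design).

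**The concern.** Six-month change in weight and waist is the short-term half of Aim 1. Ordinary regression needs a value of the dependent variable, so the planned test uses only women seen at 6 months. Weights taken later on the same women carry information about the missing value, and the 6-month test ignores it. The intention-to-treat statement does not settle how these women enter the test.

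Up to month 6 the arms differ sharply in study contact, so unequal attendance is possible. If missingness depends only on baseline weight and arm, the planned regression is unbiased and only precision suffers. If it depends on the unseen 6-month weight, the arm difference can be biased when the arms differ in how many women are missing or in how those women fared.

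The outreach sentence adds a smaller collection gap. A staff visit is already planned for secondary outcomes, yet nothing says that the primary measures are taken there when they are still outstanding.

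**Working it through.** **No figure to reproduce.** The documents give 200 women in two equal arms (Eligibility; Baseline Data Collection and Randomization). They give no SD, power, missing rate, return rate or number of home visits. All other inputs below are assumptions.

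**Who is kept.** In a simulated set of 200 women, 30 lacked a 6-month weight but had 12- and 18-month weights. The 6-month regression used 170 women. The quadratic multilevel model used all 200.

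**Precision.** Assumed: SD 6 kg, 100 per arm, two-sided 5%, 80% power, share missing p = 0.2, correlation between visits rho = 0.7, and a share l = 0.5 of the missing weighed at both later visits.

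- Detectable difference = (1.960 + 0.842) × 6 × √(2/n).
- None missing: n = 100, giving 2.38 kg.
- Planned regression: n = 80, giving 2.66 kg.
- Longitudinal model: a returning woman contributes f = 2rho²/(1 + rho) = 0.98/1.7 = 0.576 of an observation. Then n = 80 + 100 × 0.2 × 0.5 × 0.576 = 85.8, giving 2.57 kg (2.60 at rho 0.5; 2.53 at rho 0.9).
- Home weighing of a quarter or half of the missing, without the model: n = 85 or 90, giving 2.58 or 2.51 kg. With the model as well: 2.52 or 2.47 kg.

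**Bias.** Assumed: missing women did g = 3 kg worse than seen women in each arm. Using seen women only, each arm's mean is too favourable by p × g.

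- 20% missing in both arms: 0.60 − 0.60 = 0.
- 10% intervention, 30% control: 0.30 − 0.90 = −0.60, so the benefit is understated by 0.60 kg. Swapping the arms reverses the sign.
- 30% missing in both arms, with the 3 kg gap in the intervention arm only: 0.3 × 3 = 0.9, so the benefit is overstated by 0.9 kg.

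Under the longitudinal model, each arm's error is multiplied by 1 − f·l/(1 − p + p·l). For 10%/30% missing and l = 0.5:

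- Intervention: 0.30 × (1 − 0.288/0.95) = 0.209.
- Control: 0.90 × (1 − 0.288/0.85) = 0.595.
- Remaining understatement: 0.39 kg (0.48 at rho 0.5; 0.28 at rho 0.9).

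The return rate matters as much as the correlation. At rho 0.7:

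| Share returning, l | Bias left, kg |
|---|---|
| 0.5 | 0.39 |
| 0.25 | 0.48 |
| 0.1 | 0.55 |
| 0 | 0.60 |

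Home weighing alone of a quarter or half of the missing leaves 0.39 or 0.23 kg. Combined with the model at l = 0.5, it leaves 0.26 or 0.16 kg. These figures treat both the women reached at home and those who return as random shares of the missing. If they resemble attenders, the gain is smaller.

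**Which sensitivity analysis.** Take the 10%/30% case with assumed observed changes of −4 kg (intervention) and 0 kg (control).

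- Truth: intervention 0.9 × (−4) + 0.1 × (−1) = −3.7; control 0.7 × 0 + 0.3 × 3 = 0.9; benefit 4.6 kg.
- Seen women only: 4.0 kg.
- Control-based or return-to-baseline imputation: intervention 0.9 × (−4) + 0.1 × 0 = −3.6; control 0; benefit 3.6 kg. This is further from the truth than doing nothing.
- A delta shift of +3 kg in both arms recovers 4.6 kg by construction.

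**The case against.** The case against has four parts.

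- **Home outreach.** The sentence sits among the blood tests and concerns women who cannot come for the draw. It does not say that they missed the weighing. A reader might infer that the plan bars weighing at home or will lose the primary outcome there. The documents do not support this. The clinic is a default that outreach already relaxes, nothing forbids weighing, and the Manuals of Operations named under Data Management are not available and may cover it. This stands: the point is a request for one clarifying sentence.
- **Complete-case analysis.** A reader might infer that the plan specifies it. It does not. Dropping women is what regression does when no rule is given. The exposure is one contrast, and the later data can help only for women who miss month 6 and return. This narrows the point but does not remove it.
- **Direction.** A reader might infer that the result is biased towards the intervention. Nothing shows this. Reminders and payments cover both arms, eligibility requires being willing and able to attend the group meetings, and no passage says which arm would miss more.
- **Size.** Every input is assumed, and the model's gain disappears if nobody returns. This stands and limits the severity.

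**Conclusion.** The concern holds as a cheap improvement of low to moderate severity. The firm part is the analysis gap: the 6-month test of an Aim 1 outcome has no missing-data rule and, run as described, discards women whose later weights are informative. The outreach wording is a silence to be filled and is secondary.

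The size is unknown. In the illustration the precision gain is modest, 2.66 − 2.57 = 0.09 kg in detectable difference. Bias is nil if missingness and the outcome gap are equal across arms. Otherwise it has either sign, and the longitudinal model removes only part of it, by an amount that depends on the assumed return rate and correlation. That remainder is the reason for a sensitivity analysis. Confidence is high on what the text says and low on how much it matters in this trial.

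**What to change.** In Statistical Analysis:

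- Estimate the 6-month arm difference in weight and in waist from a baseline-adjusted longitudinal model with categorical time and unstructured covariance, using all randomised women with any follow-up value. Multiple imputation that uses the 12- and 18-month values is an acceptable alternative.
- Report 6-month missingness by arm.
- Add a delta-shift sensitivity analysis with the shift varied separately by arm. It should also cover women with no follow-up value, whom the longitudinal model leaves out. Do not rely on control-based or return-to-baseline imputation, which need not bracket the case of more missing controls who did worse.

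In Measures, and in the follow-up paragraph under Recruitment:

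- State that weight and waist are measured at any home outreach visit where they were not already taken, in both arms, by masked staff, with a calibrated portable scale and the same tape method. Record the location.

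The cost is a portable scale and tape, a few minutes at visits already planned, and a few sentences of text. The downsides are slight between-scale noise and a little more analysis, because categorical time differs from the planned quadratic curve.
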